9.2. Setting

The National VA Health Care Network data will be used for the current analysis. PC patients initiated relugolix will be selected for analysis based on inclusion and exclusion criteria below.

9.2.1. Inclusion criteria

Patients who met all of the following sample selection criteria will be included:

- Male with ≥ 1 diagnosis of PC (International Classification of Diseases, 10th Revision, Clinical Modification [ICD-10-CM] C61)
- Had ≥ 2 prescriptions of relugolix on or after the first observed PC diagnosis. The initiation date of relugolix will be selected as the **index date**
- At least ≥ 18 years old as of the index date
- Had continuous activity in the data for ≥ 365 days prior to the index date and ≥ 90 days since the index date (unless died within 90 days). The **baseline period** will be defined as the 365-day period prior to the index date. The **follow-up period** will be from the index date to the end of continuous eligibility, data availability, or death, whichever happened first

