 2. To assess treatment patterns among patients with PC who initiated relugolix
 3. To estimate adherence and persistence with relugolix among patients with PC who initiated relugolix
 4. To assess testosterone suppression and prostate-specific antigen (PSA) responses among ADT naïve patients with PC who initiated relugolix
 5. To describe and compare demographics and clinical characteristics between Black and non-Hispanic White patients with PC who initiated relugolix
 6. To describe and compare time to treatment changes between Black and non-Hispanic White patients with PC who initiated relugolix
 7. To estimate and compare adherence and persistence with relugolix between Black and non-Hispanic White patients with PC who initiated relugolix

Study Design: The current study will be a retrospective data analysis to describe patient characteristics, treatment patterns, adherence, and persistence among patients with PC who initiated relugolix. Adult (aged ≥ 18 years) male patients with PC who had relugolix (initiation date as the index date) will be selected from the National Veterans Affairs (VA) Health Care Network databases. Patients will be required to have continuous eligibility for at least 365 days prior to the index date and 90 days after the index date (unless died within 90 days). The baseline period will be the 365 days prior to the index date. The follow-up period will be from the index date to the earliest of death, end of continuous eligibility or end of data availability.

Population: The overall population will include PC patients who initiated relugolix. The following sample selection criteria will be used:

- Inclusion criteria:
 - Male with ≥ 1 diagnosis for PC
 - Had ≥ 2 prescriptions of relugolix on or after the first observed PC diagnosis. The identification period for relugolix use will be from December 18, 2020 to December 31, 2023
 - Index date: the initiation date of relugolix
 - At least 18 years old at the index date
 - Had continuous activity in the data for at least 365 days before the index date and 90 days following the index date (unless died within 90 days)
- Exclusion criteria:
 - Had surgical castration (bilateral orchiectomy) any time before the index date
 - Participated in clinical trials within 30 days prior to or 90 days after the index date
 - Had any other primary cancer (excluding non-melanoma skin cancer) during the baseline period

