8. RESEARCH QUESTION AND OBJECTIVES

Using data from the National VA Health Care Network databases, the study will retrospectively analyze data to describe patient characteristics and the treatment patterns of relugolix among patients with PC who initiated relugolix.

Table 1. Objectives and endpoints

Objectives	Endpoints
1. (Primary) To describe demographics and clinical characteristics of patients with PC who initiated relugolix	
Patient baseline demographics and clinical characteristics
2. (Exploratory) To assess treatment patterns among patients with PC who initiated relugolix	
Index treatment regimen distributionTreatment sequence presented by Sankey diagramTime to treatment changes by Kaplan-Meier analysis
3. (Exploratory) To estimate adherence and persistence with relugolix among patients with PC who initiated relugolix	
Adherence to relugolix defined by medication processing ratio (MPR)Adherence to relugolix defined by proportion of days covered (PDC)Persistence with relugolix by Kaplan-Meier analysis
4. (Exploratory) To assess testosterone suppression and prostate-specific antigen (PSA) responses among ADT naïve patients with PC who initiated relugolix	
Testosterone suppressionPSA response
5. (Exploratory) To describe and compare demographics and clinical characteristics between Black and non-Hispanic White patients with PC who initiated relugolix	
Patient baseline demographics and clinical characteristics by race
6. (Exploratory) To describe and compare time to treatment changes between Black and non-Hispanic White patients with PC who initiated relugolix	
Time to treatment changes by Kaplan-Meier analysis by race
7. (Exploratory) To estimate and compare adherence and persistence with relugolix between Black and non-Hispanic White patients with PC who initiated relugolix	
Adherence to relugolix defined by MPR by raceAdherence to relugolix defined by PDC by racePersistence with relugolix by Kaplan-Meier analysis by race

PFIZER CONFIDENTIAL

CT24-WI-GL02-RF02 5.0 Non-Interventional Study Protocol Template For Secondary Data Collection Study 01-
Aug-2023
Page 16 of 41

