9. RESEARCH METHODS

9.1. Study design

This is a retrospective, observational study using January 1, 2006 – December 31, 2023 data from the National VA Health Care Network databases. PC patients who initiated relugolix will be selected based on diagnosis codes, age, treatment received, and continuous activity in the health care network. The identification period for relugolix use will be from December 18, 2020 to December 31, 2023. December 18, 2020 is the approval date for relugolix in the US, and December 31, 2023 is the end of available data. The index date will be defined as the initiation date of relugolix. The baseline period will be 365 days prior to the index date (hence the start of the study period is December 18, 2019). The follow-up period will be from the index date to the earliest of death, end of continuous eligibility or end of data availability. Most of the patient characteristics will be described during the baseline period. Certain patient characteristics will be described using all data available prior to the index date (i.e., data prior to December 18, 2019 will also be used if available; see more details in Table 2). Treatment patterns, adherence, and persistence with relugolix, and PSA and testosterone responses (if sample size allows) will be assessed during the follow-up period.

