Index treatment	
Index treatment regimens include:
 
 • Relugolix monotherapy • Relugolix + NSAA only (at least 90 days of NSAA use) • Relugolix + ARPI +/- NSAA (no chemotherapy) • Relugolix + ARPI + chemotherapy • Relugolix + chemotherapy +/- NSAA (no ARPI) • Relugolix + other (no ARPI, no chemotherapy) 
Index treatment regimen will be defined based on treatments received within 30 days before the index date and within 90 days after the index date.
 
Specific treatments included in each treatment category (i.e., ADT, NSAA, ARPI, chemotherapy, immunotherapy) are described in “Treatment history” in Table 2. Other treatments include immunotherapy, radium 223, olaparib, rucaparib, talazoparib, niraparib and lutetium Lu 177 vipivotide tetraxetan.
 
Number of patients who received any radiotherapy during the index treatment will be summarized.

Variable	Operational definition
Treatment patterns of relugolix	
Treatment patterns of relugolix include:
 
• Continued relugolix as in the index treatment (regardless of discontinuation of concomitant medications)• Continued relugolix with a new add-on systemic PC treatment (excluding ADT)• Discontinued relugolix and switched to another ADT treatment• Discontinued relugolix without switching to another ADT treatment 
Add-on systemic PC treatments include:
 
• ARPI• NSAA• Chemotherapy• Immunotherapy• Radium 223• Ketoconazole• Olaparib• Rucaparib• Talazoparib• Niraparib• Lutetium Lu 177 vipivotide tetraxetan 
Add-on therapy will be evaluated from 90 days after the index period to the end of the follow-up period.

Time to treatment changes	The time to treatment changes of interest include: 
• Time to discontinuation of relugolix• Time to switching to a different ADT treatment• Time to add a new systemic PC treatment to relugolix
Treatment adherence	Adherence to relugolix post the index date will be described using both MPR and PDC: 
• MPR: Sum of the days of supply divided by the number of days between the first fill and the end of the last refill (i.e., including the days of supply from the last refill)• PDC: Sum of the non-overlapping (i.e., not double counting of overlaps) days of supply covered

Variable	Operational definition

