	divided by a pre-determined period following treatment initiation (e.g., 6 and 12 months) Adherence will be described as a continuous variable and as a binary variable (<0.80: non-adherent, ≥ 0.80 : adherent)
Treatment persistence	Persistence to relugolix will be described as the proportion of patients who did not discontinue relugolix (i.e., with a treatment gap, switch to another ADT, or death; the minimum days of treatment gap, e.g., 45 or 60 days, will be finalized based on sample size and clinical input) during the follow-up period. Treatment gaps will be assessed from the end of the days of supply of the previous prescription to the earliest of the next prescription or the end of data availability.
PSA response	Only if sample size is sufficient and among patients with at least one baseline and one follow-up period PSA measure: 
• The number and percentage of patients with $\geq 50\%$ and $\geq 90\%$ decline from the baseline PSA to any PSA measurement during the follow-up period and while on relugolix• The number and percentage of patients with the nadir PSA value during the follow-up period and on treatment of relugolix < 0.01, 0.1, and 0.2 ng/mL
Testosterone response	Only if sample size is sufficient and among patients with at least one follow-up period testosterone measure: 
• The number and percentage of patients with at least one testosterone value of <50ng/dL and <20 ng/dL during the follow-up period and while on relugolix 
If sample size is sufficient, the analysis above may be conducted among patients with at least one baseline and one follow-up period testosterone measure

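### Entry needs a second relugolix fill but persistence and PDC run from the first, so starters who stop, switch or die without refilling are left out; this is disclosed but not analysed

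*Combined protocol and SAP*

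**What the plan says.** **Entry.** Section 9.2.1 ties entry to the index date in these words: "Had ≥ 2 prescriptions of relugolix on or after the first observed PC diagnosis. The initiation date of relugolix will be selected as the". The Abstract sets the same two-fill rule. The second fill has no time limit. Section 9.2.1 waives the 90-day activity rule for patients who die within 90 days, but it does not waive the two-fill rule for them.

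**Time zero.** Section 9.1 puts the index date at the start of relugolix and adds: "The follow-up period will be from the index date to the earliest of death, end of continuous eligibility or end of data availability". Section 9.7.3 runs Kaplan-Meier persistence, and PDC at 6, 12 and 18 months (tentative), from the index date. Section 9.7.2.3 names no origin for time to discontinuation; a first-fill origin is inferred from Section 9.1.

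**Outcomes.** Table 3 in Section 9.3 treats as discontinuation a patient "with a treatment gap, switch to another ADT, or death; the minimum days of treatment gap, e.g., 45 or 60 days", with the gap length still to be settled. On measuring a gap it says: "Treatment gaps will be assessed from the end of the days of supply of the previous prescription to the earliest of the next prescription". If no further prescription comes first, the data cut-off closes the interval. The medication ratio (MPR) is "Sum of the days of supply divided by the number of days between the first fill and the end of the last refill". Table 3 adds: "Adherence will be described as a continuous variable and as a binary variable", cut at 0.80.

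**Target.** Objective 3 in Table 1 is "To estimate adherence and persistence with relugolix among patients with PC who initiated relugolix". Objectives 2, 6 and 7 name the same population.

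**Disclosure.** Section 9.9 says that the two-prescription rule selects patients who tolerated a first month and came back for a second, and that how they relate to all relugolix patients is not known.

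**The concern.** A patient enters only by doing something after time zero, namely refilling. Starters who stop, switch to another androgen deprivation therapy (ADT) or die after one fill are the earliest failures under the plan's own definition, and they are missing by design. Nobody in the cohort can die before the second fill.

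The estimates would be read as describing all who start relugolix, because the objectives say so. For that population, Kaplan-Meier persistence and PDC come out too favourable. In Objectives 6 and 7, any difference between Black and non-Hispanic White patients in never refilling would fall outside the comparison, and covariate adjustment within the two-fill cohort cannot bring back patients who were never in it.

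**Working it through.** The plan states no sample size, power or expected persistence, so there is no figure to reproduce. The check is in two parts.

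**1. Can one-fill starters be analysed under the plan's rules?** Yes. A gap is measured from the end of supply to the next prescription or the end of data, so it needs no second fill. The gap is reached at:
- 30-day first supply: 30 + 45 = day 75, or 30 + 60 = day 90. Both are within the required 90 days.
- 90-day first supply: 90 + 45 = day 135, or 90 + 60 = day 150. Both are beyond the required 90 days, so some one-fill patients would be censored and not counted as discontinued.

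Sections 9.7.1 to 9.7.7 contain no at-least-1-fill analysis, no clock started at the second fill, and no description of one-fill starters. Figure 1 is not shown and may give a count.

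**2. How large could the effect be?** All inputs here are assumptions: the share f of starters who discontinue after one fill (5% to 20%), two-fill persistence 80%, two-fill mean 6-month PDC 0.85, two-fill adherent share 75%, first supply 30 or 90 days, and 6 months taken as 180 days. Section 9.9 implies monthly fills but gives no days of supply.

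*Persistence*, past the first supply plus gap and ignoring censoring: all-starter value = (1 − f) × two-fill value.
- f = 5%: 0.95 × 0.80 = 76%
- f = 20%: 0.80 × 0.80 = 64%

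*Mean 6-month PDC*: 0.85(1 − f) + f × (supply/180). Here f counts only one-fill patients with complete 6-month follow-up, as Section 9.7.3 requires.
- 30 days (30/180 = 0.167): 0.816 at f = 5%, 0.713 at f = 20%
- 90 days (90/180 = 0.50): 0.833 at f = 5%, 0.780 at f = 20%

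One-fill patients may more often lack complete follow-up, for instance through early death. If a share q = 0.5 of them and r = 0.05 of two-fill patients lack it, then f′ = f(1 − q) / [f(1 − q) + (1 − f)(1 − r)].
- f = 5%: 0.025 / (0.025 + 0.9025) = 2.7%
- f = 20%: 0.10 / (0.10 + 0.76) = 11.6%

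Mean PDC at f′ is then 0.832 to 0.771 (30-day) or 0.841 to 0.809 (90-day).

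*Adherent share at 6 months*: the cut-off is 0.80 × 180 = 144 days, so a one-fill patient with a shorter first supply is non-adherent. 75% becomes 0.75 × 0.95 = 71% to 0.75 × 0.80 = 60%; at f′ it becomes 73% to 66%.

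*Race*: suppose f is 10% in one group and 15% in the other, with 80% two-fill persistence in both. All-starter persistence is 0.80 × 0.90 = 72% against 0.80 × 0.85 = 68%. The planned cohort would show no difference.

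*Crude discontinued proportions* (Section 9.7.2.2): if a share p of all starters have one fill, and d1 and d2 are the proportions classed as discontinued among one-fill and two-fill patients, the all-starter proportion is p·d1 + (1 − p)·d2. This exceeds d2 only when d1 > d2.

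*MPR*: after one 30-day fill it is 30/30 = 1.0, so adding one-fill patients would raise mean MPR, not lower it.

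**The case against.** The strongest reply is that this is a known and disclosed choice. Section 9.9 states it and promises that the limitations will be addressed in any write-up. The selection rules are explicit, the affected objectives are exploratory, and Section 9.5 specifies no hypotheses. Two fills also give better evidence of actual use: the plan notes that a prescription does not prove consumption, and a single recorded fill may be a drug never taken or use incompletely recorded. Every input to the size is assumed.

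Much of this stands and limits the weight of the point. It does not remove it: the disclosure says neither that persistence and PDC shift upward nor by how much, and data the study already uses can show this.

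Four stronger readings are tempting, and the documents do not support them:
- That every one-fill patient discontinued. A late starter with a long first supply may have had no time to refill and would be censored.
- That the two discontinued treatment patterns are certainly understated. They are crude proportions, and one-fill patients censored before the gap would count as continuing. Understatement is likely with monthly fills but not certain with longer first supplies.
- That a race difference is being hidden. Nothing in the documents suggests that refilling differs by race; the plan simply could not show it if it did.
- That the at-least-1-fill result is the truth. Untaken or unrecorded drug could make it understate persistence.

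Starting the clock at the second fill would give a coherent conditional estimate, but it would not answer objectives framed around everyone who initiates.

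**Conclusion.** The point holds. Provided some starters discontinue after one fill, Kaplan-Meier persistence is biased upward for all initiators. The same holds for PDC, provided some one-fill patients with complete follow-up have a first supply that covers less of the window than two-fill patients average. Time to discontinuation shares the problem if, as Section 9.1 implies, it runs from the first fill. The direction for the crude treatment-pattern proportions is conditional, and the effect on the race comparison is only possible.

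The size is unknown. The figures above are illustrations that rest on assumed one-fill shares, persistence, PDC, supply and follow-up loss. Disclosure and exploratory status make this a recommended improvement and not a flaw that invalidates the study.

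**What to change.** - Keep the two-fill analysis and label its results as patients with at least 2 fills.
- Add a sensitivity analysis of time to discontinuation, persistence and PDC in all patients with at least 1 fill, from the first fill and with usual censoring, overall and by race. Use the same adjustment covariates as the two-fill models, so that only the cohort changes.
- Report the number, race and baseline characteristics of one-fill patients (Figure 1 may already give the count). Split them into discontinued (gap, switch, death) and censored before the gap could be reached, and show that split beside the treatment-pattern proportions.
- Keep MPR on patients with at least 2 fills, since it is 1.0 after a single fill.

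The cost is a cohort flag and a second set of tables and models from data already held. The downsides are persistence that looks less favourable, PDC and MPR covering different cohorts in the added analysis, and some single fills that were never taken or were incompletely recorded. The added result should be read beside the two-fill result, not as its replacement.

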9.2.2. Exclusion criteria

Patients will not be included from the study if they:

[figure not shown]
- Had surgical castration (bilateral orchectomy) any time before the index date

PFIZER CONFIDENTIAL

CT24-WI-GL02-RF02 5.0 Non-Interventional Study Protocol Template For Secondary Data Collection Study 01-
Aug-2023
Page 17 of 41

- Had evidence of clinical trial participation within 30 days prior to the index date or within 90 days since the index date
- Had any other primary cancer (excluding non-melanoma skin cancer) during the baseline period

Figure 1. Sample selection for PC patients initiated relugolix

9.3. Variables

Baseline variables (Table 2) will be measured during the baseline period (365 days prior to the index date). Treatment patterns, adherence and persistence, and clinical variables (Table 3) will be measured during the follow-up period.

Table 2. Baseline demographic and clinical characteristic variables

Variable	Operational definition
Age	Age will be defined as of the index date and retained in the dataset as a continuous variable and a categorical variable (e.g., ≤ 59 , 60-69, 70-79, ≥ 80 years old).
Race/ethnicity	Proportion of patients that were non-Hispanic White, Black, Hispanic, other or unknown will be summarized.
Geographic regions	Proportion of patients that lived in Northeast, Midwest, South and West areas will be summarized.
Index year	A categorical variable for the index calendar year will be summarized.
Site of metastasis	Proportion of patients that had a metastatic diagnosis at the following sites: bone only, bone and node only, node

PFIZER CONFIDENTIAL

Variable	Operational definition
	only, viscera and other, will be summarized among patients with metastatic PC. All data available prior to the index date will be used.
Treatment history	
Proportion of patients who had each of the following treatments in the baseline period will be evaluated:
 
• Prostatectomy• Chronic oral corticosteroid use• Pain medication (opioids)• ADT treatment (leuprolide, degarelix, goserelin, histrelin, triptorelin)• Androgen receptor pathway inhibitor (ARPI; abiraterone, apalutamide, darolutamide, enzalutamide)• Non-steroidal anti-androgen (NSAA; bicalutamide, nilutamide, flutamide)• Chemotherapy (docetaxel, cabazitaxel, carboplatin, oxaliplatin, cisplatin, mitoxantrone)• Immunotherapy (sipuleucel-T, pembrolizumab)• Radium 223• Systemic ketoconazole• Olaparib• Rucaparib• Talazoparib• Niraparib• Lutetium Lu 177 vipivotide tetraxetan• Radiotherapy 
Treatments considered as a part of index treatment regimen will not be flagged as baseline treatments if received within 30 days prior to index date.

Time from first observed PC diagnosis date to the index date	Time from the first observed PC date in the data to the index date will be evaluated. All data available prior to the index date will be used.
NCI Charlson Comorbidity Index (CCI) score	The NCI version of the CCI score will be created during the baseline period.

Variable	Operational definition
Comorbidities	A binary variable (yes/no) will be created for patients with a diagnosis of each of the following comorbidities during the baseline period: 
• Hypertension• Hyperlipidemia• Diabetes• Urinary tract infection• Chronic obstructive pulmonary disease• Arrhythmia• Congestive heart failure• Myocardial infarction• Stroke• Angina pectoris• Inflammatory bowel disease• Acute coronary syndrome• Sexual dysfunction• Depression• Anxiety• Hot flashes• Cognitive impairment• Major adverse cardiovascula event (defined by any evidence of cardiomyopathy, heart failure, ischemic heart disease, myocardial infarction, pulmonary embolism, or stroke)
PSA	Baseline PSA value (among available) based on the PSA value closest to the index date during the 90-day window (or 180-day, to be finalized based on the number of patients with non-missing PSA value in these time frames) on or prior to the index date will be evaluated.
Testosterone	Baseline testosterone value (among available) based on testosterone value closest to the index date during the 90-day window (or 180-day; will be consistent with the time window for baseline PSA) on or prior to the index date will be evaluated.
Metastatic vs. non-metastatic PC	A binary variable for patients with metastatic vs. non-metastatic PC will be created. Metastatic PC will be

Variable	Operational definition
	defined as having evidence of metastasis during the baseline period or within 90 days since the index date.
ADT naïve vs. ADT experienced	A binary variable for patients who were ADT naïve vs. ADT experienced will be created. ADT naïve will be defined as having no records of any systemic ADT treatment ever based on all available data prior to the index date (i.e., including baseline period data and any available data prior to the baseline period). Systemic ADT treatment includes LHRH agonists and GnRH antagonists (i.e., degarelix, relugolix, goserelin, histrelin, leuprolide, triptorelin)

Table 3. Treatment patterns, adherence, persistence, and clinical variables during the follow-up period

Variable	Operational definition
Index treatment	
Index treatment regimens include:
 
 • Relugolix monotherapy • Relugolix + NSAA only (at least 90 days of NSAA use) • Relugolix + ARPI +/- NSAA (no chemotherapy) • Relugolix + ARPI + chemotherapy • Relugolix + chemotherapy +/- NSAA (no ARPI) • Relugolix + other (no ARPI, no chemotherapy) 
Index treatment regimen will be defined based on treatments received within 30 days before the index date and within 90 days after the index date.
 
Specific treatments included in each treatment category (i.e., ADT, NSAA, ARPI, chemotherapy, immunotherapy) are described in “Treatment history” in Table 2. Other treatments include immunotherapy, radium 223, olaparib, rucaparib, talazoparib, niraparib and lutetium Lu 177 vipivotide tetraxetan.
 
Number of patients who received any radiotherapy during the index treatment will be summarized.

Variable	Operational definition
Treatment patterns of relugolix	
Treatment patterns of relugolix include:
 
• Continued relugolix as in the index treatment (regardless of discontinuation of concomitant medications)• Continued relugolix with a new add-on systemic PC treatment (excluding ADT)• Discontinued relugolix and switched to another ADT treatment• Discontinued relugolix without switching to another ADT treatment 
Add-on systemic PC treatments include:
 
• ARPI• NSAA• Chemotherapy• Immunotherapy• Radium 223• Ketoconazole• Olaparib• Rucaparib• Talazoparib• Niraparib• Lutetium Lu 177 vipivotide tetraxetan 
Add-on therapy will be evaluated from 90 days after the index period to the end of the follow-up period.

Time to treatment changes	The time to treatment changes of interest include: 
• Time to discontinuation of relugolix• Time to switching to a different ADT treatment• Time to add a new systemic PC treatment to relugolix
Treatment adherence	Adherence to relugolix post the index date will be described using both MPR and PDC: 
• MPR: Sum of the days of supply divided by the number of days between the first fill and the end of the last refill (i.e., including the days of supply from the last refill)• PDC: Sum of the non-overlapping (i.e., not double counting of overlaps) days of supply covered

Variable	Operational definition
	divided by a pre-determined period following treatment initiation (e.g., 6 and 12 months) Adherence will be described as a continuous variable and as a binary variable (<0.80: non-adherent, ≥ 0.80 : adherent)
Treatment persistence	Persistence to relugolix will be described as the proportion of patients who did not discontinue relugolix (i.e., with a treatment gap, switch to another ADT, or death; the minimum days of treatment gap, e.g., 45 or 60 days, will be finalized based on sample size and clinical input) during the follow-up period. Treatment gaps will be assessed from the end of the days of supply of the previous prescription to the earliest of the next prescription or the end of data availability.
PSA response	Only if sample size is sufficient and among patients with at least one baseline and one follow-up period PSA measure: 
• The number and percentage of patients with $\geq 50\%$ and $\geq 90\%$ decline from the baseline PSA to any PSA measurement during the follow-up period and while on relugolix• The number and percentage of patients with the nadir PSA value during the follow-up period and on treatment of relugolix < 0.01, 0.1, and 0.2 ng/mL
Testosterone response	Only if sample size is sufficient and among patients with at least one follow-up period testosterone measure: 
• The number and percentage of patients with at least one testosterone value of <50ng/dL and <20 ng/dL during the follow-up period and while on relugolix 
If sample size is sufficient, the analysis above may be conducted among patients with at least one baseline and one follow-up period testosterone measure

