9.4. Data sources

January 1, 2006 to December 31, 2023 data from the National VA Health Care Network will be used for this study. This network is the US's largest integrated health care system with over 1,700 sites of care, serving approximately 8.76 million veterans each year. The VA Health System Corporate Data Warehouse (CDW) includes all medical encounter information in the VA, comprised of medical centers, community-based outpatient clinics, community-living centers, veteran centers, and domiciliaries. The VA CDW stores data in separate databases, one for each type of clinical information - inpatient medication, inpatient laboratory, inpatient admission, outpatient medication, outpatient laboratory, outpatient visits, etc. The databases provide demographic information and contain comprehensive services, including primary care, specialty care, inpatient care, rehabilitation, long-term care, home care, and other services, to military veterans. The database also includes date of death. The date of death is extracted from the VA electronic health record systems and verified by official sources, including VA facilities, death certificates, and National Cemetery Administration. Information on CDW, including date of death, is updated on a daily base. Cause of death is not available on CDW.

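### Prostatectomy and radiotherapy are counted only in the 365 days before relugolix, so the primary-objective table cannot show how many men had any earlier recorded local therapy.

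*Combined protocol and SAP*

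**What the plan says.** Section 9.3 sets the general rule: "Baseline variables (Table 2) will be measured during the baseline period (365 days prior to the index date"). In Table 2 the treatment history row applies it to every listed item: "Proportion of patients who had each of the following treatments in the baseline period will be evaluated". Prostatectomy is the first item on the list and radiotherapy the last.

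Section 9.1 allows exceptions: "Certain patient characteristics will be described using all data available prior to the index date". It adds that "data prior to December 18, 2019 will also be used if available; see more details in Table 2". Three rows of Table 2 are marked in this way: site of metastasis, time from first observed diagnosis to index, and ADT naïve status. The last requires "no records of any systemic ADT treatment ever based on all available data prior to the index date" and spells this out as "including baseline period data and any available data prior to the baseline period". The treatment history row carries no such mark. Separately, section 9.2.2 excludes men with bilateral orchiectomy at any time before index.

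On the data themselves, section 9.4 states: "January 1, 2006 to December 31, 2023 data from the National VA Health Care Network will be used for this study". Section 9.1 states: "The identification period for relugolix use will be from December 18, 2020 to December 31, 2023".

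**The concern.** The primary objective is to describe the men who start relugolix, and the abstract lists previous treatment among the characteristics without naming a window. Many of the listed items are drug treatments, for which recent use is a natural question. Removal of the prostate is different: it is permanent, and whether it was done matters more to the description than whether it was done in the last year. Much the same can be said of a past course of radiotherapy. A one-year flag puts a man treated several years ago in the same cell as a man with no local therapy at all.

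At stake is whether the main table answers a question that its readers will bring to it, namely how many men starting relugolix had already had local treatment. The same row is compared by race under section 9.7.5. There, a difference in when local therapy was given could be read as a difference in whether it was given.

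**Working it through.** The plan states no figure for prior local therapy, so there is none to reproduce. The check has three parts.

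**1. Is earlier local therapy captured anywhere else?**

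| Item | Look-back | Where |
|---|---|---|
| Prostatectomy, radiotherapy | 365 days | 9.3, Table 2, treatment history |
| Site of metastasis | all prior data | 9.3, Table 2 |
| Time from first observed diagnosis | all prior data | 9.3, Table 2 |
| ADT naïve status | all prior data | 9.3, Table 2 |
| Bilateral orchiectomy (exclusion) | any time before index | 9.2.2 |
| Radiotherapy during index treatment | regimen window of 30 days before to 90 days after index | 9.3, Table 3 |

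Only the last row mentions local therapy again, and it reaches back no further than the baseline period. The limitations in section 9.9 do not mention the short window. Earlier prostatectomy and radiotherapy are therefore not recovered.

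**2. How much recorded history is left unused?** The formula is calendar look-back = index date minus 1 January 2006, the start of the data.

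- Earliest index date, 18 December 2020: 5,465 days, or 5,465 / 365.25 = 15.0 years. The planned window is 365 / 5,465 = 6.7% of it.
- Index date 2 October 2023, the last that allows 90 days before the data end on 31 December 2023: 6,483 days, or 17.7 years. The planned window is 365 / 6,483 = 5.6% of it.

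These are upper limits. The history actually available for a man depends on when he entered the VA data, and section 9.2.1 guarantees only 365 days.

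**3. Direction and size.** Let p be the share of men with any recorded local therapy before index, and f the share of those who had it within 365 days. Then

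- share shown by the planned row = p × f
- share not shown = p × (1 − f)

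Since f cannot exceed 1, the planned row cannot exceed p. The documents give neither p nor f, so the values below are assumptions used only for illustration.

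| p | f | Shown, p × f | Not shown, p × (1 − f) |
|---|---|---|---|
| 40% | 10% | 4% | 36 points |
| 40% | 30% | 12% | 28 points |
| 40% | 50% | 20% | 20 points |
| 20% | 90% | 18% | 2 points |
| 60% | 10% | 6% | 54 points |

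The last two rows are the extremes for p from 20% to 60% and f from 10% to 90%.

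**The case against.** The strongest reply is that the plan contains no error. It defines a proportion over a stated window, says openly that most characteristics come from the baseline period, and observes every man over the same length of time. An ever/never variable would lose that evenness. It would also call men never treated when their treatment took place before they entered the VA data or outside it. Appendix Table 1 lists no codes for either treatment, so the work is more than a change of date.

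Most of this stands, and it limits the point in three ways.

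- A reader might infer that men treated earlier will be reported as never having had local therapy. The documents do not support this. The planned statistic is specific to its window, and no category of never treated appears.
- A reader might infer that a man treated years ago and now starting relugolix will look the same as one newly diagnosed. That too goes too far. Time from first observed diagnosis uses all prior data and would usually separate the two. It does not, however, tell a long-known cancer with local therapy from one without.
- A reader might infer that the adjusted models or the PSA results will be distorted. Covariates in sections 9.7.6 and 9.7.7 are still to be chosen from the section 9.7.5 findings and clinical input, so nothing says that these flags enter. The PSA analysis in section 9.7.4 is conditional on sample size and does not use treatment history.

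The reply does not touch the gap itself. A correct one-year figure still leaves the question of any prior local therapy unanswered. Unequal look-back is something the plan already accepts for ADT naïve status and time since diagnosis.

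**Conclusion.** The point holds as a gap in the primary-objective description, not as an error in a planned figure. Local therapy more than 365 days before index is not captured, although the data could reach back as far as 15.0 to 17.7 years and three neighbouring variables and one exclusion already use that history.

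The direction is certain with respect to recorded therapy: the planned proportions cannot exceed the share with any prior record. That they fall short of it is probable, because this requires only that some men were treated more than a year before index. The size is undetermined. The range of 2 to 54 points rests wholly on assumed values of p and f and should not be cited as an estimate.

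The improvement is cheap and worth making before the analysis dataset is built.

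**What to change.** In Table 2:

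- Add two flags, *any recorded prostatectomy* and *any recorded radiotherapy*, taken from all data available before the index date.
- Keep the two existing flags and label them *within 365 days*. Apply the table's 30-day rule on index-regimen treatments in the same way to both sets, so that the recent flag is always contained in the longer one.
- Label the absence of a record *no record*, not *never*.
- Report the length of available history before index, overall and by race.

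In the analysis sections, describe the new flags under 9.7.1 and 9.7.5, and make them available as candidate covariates in 9.7.6 and 9.7.7. Drug treatments can stay on the 365-day window. Add a sentence to section 9.9 stating that treatment outside or before the VA data is missed.

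The cost is two binary variables from a data source already in the plan, plus procedure code lists for both treatments. Codes are needed even for the flags as planned, since Appendix Table 1 gives none; for the longer look-back they must also cover the earlier years. The remaining drawback is that look-back differs between men, so the new flags should be read beside the length of history.
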